2.3. Benefit/Risk Assessment

The potential risk assessment and mitigation strategy for the administration of otilimab in this protocol is outlined below.

2.3.1. Risk Assessment

More detailed information about the known and expected benefits and risks and reasonably expected adverse events of otilimab may be found in the Investigator’s Brochure (IB). The assessment of potential risks and mitigation strategy for the administration of otilimab in this protocol is outlined below.

Potential Risk of Clinical Significance	Summary of Data/Rationale for Risk	Mitigation Strategy
Study Intervention(s) Otilimab		

Cytokine release syndrome (CRS)
	
CRS is a systemic inflammatory response caused by the release of inflammatory cytokines, such as IL-6, tumor necrosis factor alpha (TNFα), by lymphocytes (B cells, T cells, and/or natural killer cells) and/or myeloid cells (macrophages, dendritic cells, and monocytes). This can lead to a constellation of clinical symptoms including fever, flu-like symptoms, hypotension, to severe inflammatory syndrome leading to widespread organ dysfunction, even death. It is not expected that the inhibition of GM-CSF signaling, by administration of otilimab, would carry the risk of directly inducing CRS.
 
Pre-Clinical Data GM-CSF neutralization in CAR T-cell assays or in vivo models inhibited cytokine release [Sachdeva, 2019; Sterner, 2019]. In vitro otilimab showed variable results, with evidence of cytokine elevation at elevated levels of otilimab (50 and 100 μg/mL). Primate toxicology studies demonstrated no evidence of CRS with concentrations at C_{max} of 2,690 μg/mL (54x higher than anticipated human levels) and substantial safety margin for AUCs.
	
Mitigation:
 
Part 1:
 
 • To mitigate the uncertainty around safety and tolerability of otilimab IV, dosing will occur in an initial safety cohort of 20 non-mechanically ventilated participants, and these participants will be closely monitored and dosed in a staggered manner (see Section 4.1). • Unless a safety signal is identified during the ongoing safety review by the GSK SRT and periodic review by the IDMC, enrolment of the main cohort of participants will be initiated. 
Part 1 and Part 2
 
 • Careful dose selection. • Exclusion of participants who do not require oxygen therapy, and estimated GFR \leq30 mL/min/1.73m² (Section 5.3 and Section 5.4, Exclusion Criteria). 
Monitoring:
 
Part 1
 
 • All participants will be hospitalized during infusion and will be closely monitored for signs and symptoms of CRS (defined as a worsening

Potential Risk of Clinical Significance	Summary of Data/Rationale for Risk	Mitigation Strategy
	
Clinical Data: There has been no evidence of cytokine release or symptoms suggestive of CRS in any human study with otilimab or in Part 1 of the study. PK data from IV administration of absolute doses of otilimab 90 mg or higher is available from a total of 46 HVs and patients, with a maximum concentration of 56 µg/mL in one HV.
	
of the CTCAE CRS Grade, Section 7.4.7.1. Cytokine Release Syndrome) within 6 hours of infusion.
 
 • CRS (considered not related to COVID-19) is categorized as an AESI. • Evidence of CRS that occurs within 6 hours of infusion and demonstrated as worsening of CRS. • In the event of CRS (considered not related to COVID-19), investigators should follow institutional guidelines for symptom management. • In the event that new onset of CRS (considered not related to COVID-19) is suspected, the medical monitor must be notified immediately and under no circumstance can this exceed 24 hours, and the event must also be reported within 24 hours as an AE or an SAE. 
Part 2
 
 • All participants will be hospitalized during infusion and will be closely monitored for signs and symptoms of CRS (Section 7.4.7.1) within 6 hours of the start of infusion. • CRS (considered not related to COVID-19) of new onset or worsening of CRS grade, and occurring within 6 hours from the start of infusion is categorized as an AESI and must be reported as an AE or SAE. • If CRS (considered not related to COVID-19) does occur, the medical monitor must be notified immediately (within 24 hours).

Serious hypersensitivity reactions
	
There is a potential risk of hypersensitivity reactions, including anaphylaxis, during and following the administration of protein-based products, such as otilimab.
	
Mitigation:
 
 • Exclusion of participants with a history of allergic reaction, including anaphylaxis to any previous treatment with an anti-GM-CSF therapy (Section 5.3 and Section 5.4 Exclusion Criteria)

Potential Risk of Clinical Significance	Summary of Data/Rationale for Risk	Mitigation Strategy


Potential Risk of Clinical Significance	Summary of Data/Rationale for Risk	Mitigation Strategy
		
 • Currently receiving chronic oral corticosteroids for a non-COVID-19 related condition in a dose higher than prednisone 10 mg or equivalent per day. 
Monitoring:
 
 • Serious infections are categorized as AESIs. Note: An infection is considered serious if it meets any of the regulatory definitions of serious which include fatal, life-threatening, prolongation of existing hospitalization (since subjects are already hospitalized) or re-hospitalization, and if in the opinion of the investigator the infection meets other serious criteria. • Participants will be hospitalized under direct medical supervision and closely monitored for signs of infection as part of SoC with appropriate diagnostic tests and antibiotic treatment, as necessary. • Routine laboratory assessments will be obtained throughout hospitalization.

AESI=Adverse Event of Special Interest, ANC=Absolute Neutrophil Concentration, AUC=Area Under the Curve, CAR=Chimeric Antigen Receptor, C_{max}=Maximum Concentration, CRS=Cytokine Release Syndrome, CTCAE=Common Terminology Criteria for Adverse Events, DMARDs=Disease Modifying Antirheumatic Drugs, HV=Healthy Volunteer, GFR=Glomerular Filtration Rate, IDMC=Independent Data Monitoring Committee, SC=Subcutaneous.

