14. Currently receiving chronic oral corticosteroids for a non-COVID-19 related condition in a dose higher than prednisone 10 mg or equivalent per day.
15. Treatment with an investigational drug within 30 days of randomization.

PRIOR/CONCURRENT CLINICAL STUDY EXPERIENCE

16. Participating in other drug clinical trials, including for COVID-19.

DIAGNOSTIC ASSESSMENTS

17. Aspartate aminotransferase (AST) or alanine aminotransferase (ALT) >5x upper limit of normal (ULN).
18. Platelets <50,000/mm³.
19. Hemoglobin ≤9 g/dL.
20. Absolute neutrophil count (ANC) <1.5 x 10⁹/L (neutropenia ≥ Grade 2).
21. Estimated GFR ≤30 mL/min/1.73m².

OTHER CRITERIA

22. Pregnant or breastfeeding females.

5.4. Exclusion Criteria – Part 2

Participants are excluded from Part 2 of the study if any of the following criteria apply:

RELATED TO SEVERE PULMONARY COVID-19 RELATED DISEASE

1. Progression to death is imminent and inevitable within the next 48 hours, irrespective of the provision of treatments, in the opinion of the investigator.
2. Multiple organ failure according to the investigator's judgement or a Sequential Organ Failure assessment (SOFA score) >10 if intubated in the ICU.
3. Extracorporeal membrane oxygenation (ECMO) hemofiltration/dialysis, or more than one inotrope/vasopressor of any class.

CONCOMITANT MEDICAL CONDITIONS

4. Current serious or uncontrolled medical condition (*e.g.* significant pulmonary disease [such as severe COPD or pulmonary fibrosis], heart failure [NYHA class III or higher], severe renal dysfunction, acute myocardial infarction or acute cerebrovascular accident within the last 3 months), severe dementia, severe disability, or abnormality of clinical laboratory tests that, in the investigator's judgment, precludes the participant's safe participation in and completion of the study.
5. **Untreated** systemic bacterial, fungal, viral, or other infection (other than SARS-CoV-2).
6. Known active tuberculosis (TB), history of untreated or incompletely treated active or latent TB, suspected or known extrapulmonary TB.

7. Known HIV regardless of immunological status.
8. Known HBsAg and/or anti-HCV positive (patients demonstrating a sustained virologic response (SVR) are not excluded from participation).
9. Currently receiving radiotherapy, chemotherapy (hormone based therapies are permitted) or immunotherapy for malignancy.

PRIOR MEDICATIONS/TREATMENTS

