7.4.7. Adverse Events of Special Interest

The potential risks of otilimab are discussed in Section [2.3](#).

Adverse events of special interest (AESI) include:

- Cytokine release syndrome (CRS) (not related to COVID-19 [see Section [7.4.7.1](#)])
- Serious hypersensitivity reactions
- Infusion site reactions
- Neutropenia \geq Grade 3 ($<1.0 \times 10^9/L$)
- Serious infections

AESIs should be reported as AEs or SAEs, as appropriate. Please refer to Section [9.3](#) ([Appendix 3](#)) and the SRM.

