9.3.1. Definition of AE

AE Definition

 An AE is any untoward medical occurrence in a clinical study participant, temporally associated with the use of a study intervention, whether or not considered related to the study intervention. NOTE: An AE can therefore be any unfavorable and unintended sign (including an abnormal laboratory finding), symptom, or disease (new or exacerbated) temporally associated with the use of a study intervention.

Events Meeting the AE Definition

 Any abnormal laboratory test results (hematology, clinical chemistry, or urinalysis) or other safety assessments (e.g., ECG, radiological scans, vital signs measurements), including those that worsen from baseline, considered clinically significant in the medical and scientific judgment of the investigator (i.e., not related to progression of underlying disease). Exacerbation of a chronic or intermittent pre-existing condition including either an increase in frequency and/or intensity of the condition. New conditions detected or diagnosed after study intervention administration even though it may have been present before the start of the study. Signs, symptoms, or the clinical sequelae of a suspected intervention- intervention interaction. Signs, symptoms, or the clinical sequelae of a suspected overdose of either study intervention or a concomitant medication. Overdose per se will not be reported as an AE/SAE unless it is an intentional overdose taken with possible suicidal/self-harming intent. Such overdoses should be reported regardless of sequelae. "Lack of efficacy" or "failure of expected pharmacological action" per se will not be reported as an AE or SAE. Such instances will be captured in the efficacy assessments. However, the signs, symptoms, and/or clinical sequelae resulting from lack of efficacy will be reported as AE or SAE if they fulfil the definition of an AE or SAE.

Events NOT Meeting the AE Definition

 Any clinically significant abnormal laboratory findings or other abnormal safety assessments which are associated with the underlying disease, unless judged by the investigator to be more severe than expected for the participant's condition. The disease/disorder being studied or expected progression, signs, or symptoms of the disease/disorder being studied, unless more severe than expected for the participant's condition.

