4.5.2.1. Adverse Events of Special Interest

The following will be considered adverse events of special interest (AESI) for the purpose of analyses:

- Cytokine release syndrome (CRS)
- Serious hypersensitivity reactions
Note: these will be adjudicated by the SRT.
- Infusion site reactions
- Neutropenia \geq Grade 3 ($< 1.0 \times 10^9/L$)
- Serious infections

Listings of event characteristics will be provided for each AESI respectively. For AESIs with more than 8 events a summary of event characteristics will be provided for each AESI respectively, including number and percentage of participants with any event, number and percentage of events, maximum intensity, outcomes and the action taken for the event. The worst-case approach will be applied at participant level for the maximum intensity, *i.e.* a participant will only be counted once as the worst case from all the events experienced by the participant.

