4.5.2.2. Adverse Event Groups of Interest

Standardized MedDRA Queries (SMQ) will be used, if available, to identify all AEs in the following Adverse Event groups of interest:

- Pneumonia
- Sepsis
- Opportunistic Infections
- Thromboembolic Events
- Pulmonary Embolism

An SMQ is not available for pulmonary embolism, therefore a grouping for pulmonary embolism will be created by review of AE PTs reported for the study and PT will be identified that are indicative of PE.

Summaries of All AEs and SAEs by PT group and PT will be presented. These will also be produced for each of the clinical statuses at baseline. Analysis of the PT groups of interest will follow the approach for the analysis of AEs in PTs (including that if a subject has more than one event in each PT group of interest, they will be counted once).

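### The serious-infection AESI and the Pneumonia group state no COVID-19 exclusion, so reported disease worsening can dilute or mask an excess of secondary infections

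*Protocol*

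**What the plan says.** Protocol 7.4.7 and Part 2 SAP 4.5.2.1 both list "Serious infections" as an adverse event of special interest, with no limit on the infecting organism. The monitoring note in protocol 2.3.1 adds only a seriousness rule: "An infection is considered serious if it meets any of the regulatory definitions of serious which include fatal, life-threatening, prolongation of existing hospitalization". SAP 4.5.2.1 plans a listing for each AESI. For any AESI with more than 8 events it also plans a summary that includes the number and percentage of participants with any event.

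SAP 4.5.2.2 defines further groups, among them Pneumonia, Sepsis and Opportunistic Infections: "Standardized MedDRA Queries (SMQ) will be used, if available, to identify all AEs in the following Adverse Event groups of interest". No COVID-19 exclusion is stated for any of them. On display it says "Summaries of All AEs and SAEs by PT group and PT will be presented".

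Elsewhere the protocol does separate the background disease. The 7.4.7 list has "Cytokine release syndrome (CRS) (not related to COVID-19", and Part 2 exclusion criterion 5 refers to untreated "systemic bacterial, fungal, viral, or other infection (other than SARS-CoV-2").

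Two clauses in protocol 9.3.1 decide what can reach these tables. Among events that are not AEs it lists "The disease/disorder being studied or expected progression, signs, or symptoms of the disease/disorder being studied, unless more severe than expected for the participant's condition". It also says that "the signs, symptoms, and/or clinical sequelae resulting from lack of efficacy will be reported as AE or SAE if they fulfil the definition".

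**The concern.** Inclusion criterion 2 for Part 2 means that every participant is in hospital with COVID-19 pneumonia. The condition under treatment is itself an infection and a pneumonia, so the event of interest and the background disease overlap more here than for any other AESI. Yet this item has neither the qualifier that CRS has in the protocol list nor the adjudication note that the SAP attaches to serious hypersensitivity reactions.

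For a drug that blocks GM-CSF, the safety question is whether other infections become more frequent. COVID-19 worsening is the efficacy outcome and should fall if the drug works. A count that mixes the two can hide an increase in one behind a decrease in the other.

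The summary carries weight. Protocol 2.3.2 cites the absence of safety concerns in Part 1, AESIs included, in support of Part 2. In Part 2 the IDMC reviews safety data only (protocol 8.5). SAP 4.5.2.3 repeats the AESI and group summaries by sex, baseline clinical status and age.

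**Working it through.** **Route into the tables.** An AESI is reported as an AE or SAE (protocol 7.4.7), so it must first meet 9.3.1.

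1. Expected progression of COVID-19 is not an AE and does not enter.
2. Progression that the investigator judges more severe than expected is an AE. If it is fatal, life-threatening or prolongs hospitalization, it is also serious.
3. Sequelae of lack of efficacy enter if they meet the AE or SAE definition.
4. Neither SAP 4.5.2.1 nor 4.5.2.2 states a rule that separates the events from steps 2 and 3 from secondary infections.

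**Inputs from the plan.** Protocol 8.2 assumes a placebo response of 45% and a 15-point gain for Part 2. Failure is therefore 1 − 0.45 = 55% on placebo and 1 − 0.60 = 40% on otilimab. As a check on these inputs, the pooled two-proportion formula at one-sided 2.5% and 80% power gives

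n = [1.960·√(2·0.525·0.475) + 0.842·√(0.45·0.55 + 0.60·0.40)]² / 0.15² ≈ 173 per arm,

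or 346 in total, which is the plan's figure.

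**Assumed inputs.** The documents give no infection rates. I take other serious infections as s = 8% on placebo and 16% on otilimab (true relative risk 2.0), independent of COVID-19 worsening. A share f of primary-endpoint failures is also reported as serious COVID-19 infection, so c = f × failure rate.

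**Formula.** P(any event) = 1 − (1 − c)(1 − s).

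| f | c, placebo / otilimab | Any event, placebo | Any event, otilimab | RR |
|---|---|---|---|---|
| 10% | 5.5% / 4.0% | 1 − 0.945·0.92 = 13.06% | 1 − 0.96·0.84 = 19.36% | 1.48 |
| 25% | 13.75% / 10.0% | 1 − 0.8625·0.92 = 20.65% | 1 − 0.90·0.84 = 24.40% | 1.18 |
| 50% | 27.5% / 20.0% | 1 − 0.725·0.92 = 33.30% | 1 − 0.80·0.84 = 32.80% | 0.98 |

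**Dilution apart from masking.** Now suppose otilimab has no effect on COVID-19, so that both arms have the placebo value of c. The otilimab rates become 1 − 0.945·0.84 = 20.62%, 1 − 0.8625·0.84 = 27.55% and 1 − 0.725·0.84 = 39.10%. The relative risks are 1.58, 1.33 and 1.17. This is plain dilution toward 1; the further fall in the table comes from the assumed benefit.

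**Other assumed rates.** With other infections at 10% vs 20% and equal c of 5%, 10%, 20% and 40%, the relative risk is 1.66, 1.47, 1.29 and 1.13. If c falls from 20% on placebo to 10% on otilimab, both arms show 28% and the relative risk is 1.0.

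**The case against.** The strongest reply is that 9.3.1 already does the filtering. The disease under study and its expected progression are not AEs. Conditions that begin after consent but before dosing are medical history (7.4.1). Protocol 7.4.6 allows for deaths that are not SAEs. The lack-of-efficacy clause applies only where the AE or SAE definition is met. This stands as a limit: a reader might infer that any worsening of COVID-19 is counted as a serious infection, and the text does not say so. The filter is incomplete, however. It turns on each investigator's view of what is more severe than expected, and no later analysis rule deals with what passes.

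Second, other displays help. Each AESI is listed by event, the groups are shown by preferred term, Sepsis and Opportunistic Infections are separate, and deaths are summarized by whether COVID-19 contributed (SAP 4.5.3.1). A reader might infer that the infection counts could not be recovered. That goes too far, because the AESI listings allow COVID-19 events to be set aside. But that would be done after unblinding, on terms chosen with the results in view.

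Third, the illustration is not anchored in data. Participants enter in category 5 or 6, so a Day 28 failure may simply not have improved, which need not be an SAE. No formal safety hypothesis is tested (protocol 8.4.5). Both points are fair: the figures show direction and possible size, not an expected result.

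Fourth, relevant text may lie elsewhere. Part of the infections row in protocol 2.3.1 is not in the text available here. The study reference manual, the output and programming specification and the SMQ contents are not available either. Whether COVID-19 terms fall in the Pneumonia group is therefore not established; the SAP only fails to exclude them.

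**Conclusion.** The concern holds as a gap in definition. Neither the serious-infection AESI nor the Pneumonia group states a COVID-19 exclusion, and the AE definition closes the gap only in part. COVID-19 worsening that is reported as an SAE can enter the participant count and weaken a real excess of secondary infections.

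Under the assumptions above, a true relative risk of 2.0 appears as about 1.48, 1.18 or 0.98 when 10%, 25% or 50% of failures are so reported. The reporting shares, infection rates and independence are all assumed. Only the 55% and 40% follow from the plan.

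A reader might also infer that mixing the two kinds of event would suggest harm when otilimab has no benefit. It would not: equal additions to both arms pull the ratio toward 1. A push toward apparent harm would require COVID-19 outcomes to be worse on otilimab.

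The primary efficacy analysis is unaffected. The point concerns how well the planned safety tables can show an infection signal, and it should be settled before the Day 28 unblinding.

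**What to change.** In Part 2 SAP 4.5.2.1 and 4.5.2.2, summarize serious infections and the Pneumonia group in three rows: excluding COVID-19/SARS-CoV-2 preferred terms, those terms alone, and combined. Fix the list of terms on blinded review before the Day 28 unblinding described in SAP 4.7, and cite the progression rule in protocol 9.3.1. Carry the same rows into the subgroup summaries of SAP 4.5.2.3.

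Add a matching qualifier to the serious-infections item in protocol 7.4.7, worded so that AE and SAE reporting itself does not change. Keeping all three rows loses nothing: any worsening of the SARS-CoV-2 infection stays visible beside the secondary infections.

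The cost is SAP and protocol wording, one preferred-term list and extra table rows. No new data are needed.

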2.3.2. Benefit Assessment

Otilimab is currently in Phase 3 clinical development for the treatment of RA, at weekly doses of 90 and 150 mg SC for up to 12 months in pivotal studies and thereafter eligible for treatment in a long-term extension study.

In completed studies (IV and SC), cumulatively 447 patients and healthy volunteers (HV) have received otilimab (326 RA patients, 25 multiple sclerosis (MS) patients, 22 hand osteoarthritis patients, and 74 HVs).

Although otilimab has not been studied before in this acutely ill population, there is biologic rationale which supports the use of otilimab in the treatment of COVID-19 patients with pulmonary complications.

GM-CSF can act as a proinflammatory cytokine that promotes myeloid cell survival and polarizes monocytes/macrophages into pro-inflammatory phenotypes that are primed to produce pro-inflammatory cytokines including TNF α , IL-1 β and IL-6. GM-CSF also extends neutrophil survival, primes the oxidative burst, enhances phagocytosis and promotes neutrophil adhesion to endothelial cells and neutrophil trafficking to sites of inflammation.

COVID-19 ICU patients have increased circulating numbers of IL-6⁺ monocytes, CD14⁺CD16⁺ monocytes and GM-CSF⁺IFN γ ⁺ helper T cells compared with non-ICU COVID-19 patients. Once hypoxia occurs, stopping the systemic hyper-inflammatory processes to limit further damage to lung and other organs would be the most important therapeutic approach. Preclinical data suggest that elevated levels of GM-CSF in the lung could be more beneficial in the early stages of disease and may play a role in disease resolution by helping control viral titer, restore or maintain the lung barrier function, and return to tissue homeostasis. As the disease progresses, suppressing the systemic hyper-inflammatory processes would be a priority and where otilimab could be beneficial. Therefore, a single dose of otilimab in patients with pneumonia and oxygenation impairment, would be expected to inhibit inflammation and still allow sufficient GM-CSF levels in the lung during the recovery phase.

Update for Part 2

Otilimab has been tested in patients with severe pulmonary COVID-19 related disease in Part 1 of this study, with substantial clinical benefit in the pre-defined stratification group of participants 70 to <80 years old, with no safety concerns identified (including all AESIs) in either the overall study population or the pre-defined stratification group of participants 70 to <80 years old.

